11.4 Power analysis and sample size calculation

Sample size and power considerations are not relevant here as this is an open-label extension study design.

11.5 Accrual number request

Because up to 85 patients can be enrolled into IPPoMS study (to yield 66 subjects who complete 2 years of dosing), theoretically up to 85 subjects can be enrolled into IPPoMS-E study.

12. HUMAN SUBJECT PROTECTION

12.1 Subject selection

The investigational nature and objectives of this trial, the procedures and treatments involved, as well as the attendant risks, discomforts, and potential benefits will be carefully explained to the patient. A signed consent form will be obtained by the principal investigator or an associate investigator. It will be carefully explained to patients that they may withdraw from the study at any time, for any reason.

All adult PP-MS patients fulfilling all inclusion criteria and for whom none of the exclusion criteria are applicable, irrespective of gender or race are included in the IPPoMS trial. All patients who conclude IPPoMS trial will be eligible for IPPoMS-E study.

Patients who are unable to give informed consent will be excluded, as these patients were also excluded in the IPPoMS Trial, and therefore will not qualify for this extension trial.

12.2 Justification for exclusion of children

No patients under the age of 18 are included in IPPoMS and therefore this is not relevant to this open-label extension study. Patients under the age of 18 were excluded in the IPPoMS trial since the incidence of MS in this age group is extremely low and PP-MS is virtually non-existent. Consequently, insufficient numbers of patients in that age range would be available to provide reliable data.

12.3 Study safeguards

Because the effects of idebenone therapy on pregnancy and breastfeeding are unknown, patients able to become pregnant or able to father a child will be required to use appropriate methods of contraception for the trial duration and all women able to become pregnant will be evaluated with a pregnancy test every 6 months and before any MRI. Women over age 55 who have not had a period for one year will be considered menopausal and will not need pregnancy testing or contraception. Women under the age of 55 will undergo pregnancy testing and will be required to use appropriate methods of contraception for the trial duration, unless there is a history of surgical menopause.

13. BENEFITS

13.1 Direct Benefit:

Participants may receive direct therapeutic benefit from participation in this study

13.2 Indirect Benefit:

The study will yield generalizable knowledge about the drug and disease state and will aid in developing future neuroprotective therapeutic trials in MS patients

14. SUMMARY/CLASSIFICATION OF RISK:

Classification of risk for the study as a whole: The risk is classified as more than minimal risk.

This is a reasonable risk in relation to the anticipated potential therapeutic benefit in a patient population for which there are currently no therapeutic agents with proven benefit and for obtaining generalizable knowledge that will facilitate more rapid screening of novel neuroprotective agents in low-inflammatory progressive MS subtypes.

15. CONSENT DOCUMENTS AND PROCESS

Prior to any testing under this protocol, including screening or pre-treatment tests and evaluations, written informed consent will be obtained from the subject in accordance with local practice and regulations. Study investigators (As noted in section 12.4) will obtain informed consent.

The background of the proposed study and the benefits and risks of the procedures and study will be explained to the subject. A copy of the informed consent document signed and dated by the subject will be given to the subject. Confirmation of a subject's informed consent will also be documented in the subject's medical records prior to any testing under this protocol, including screening or pre-treatment tests and evaluations.

Information that is gained through this study will be available to the participating patients.

Consent forms are attached.

16. DATA AND SAFETY MONITORING

16.1 Monitoring plan for the study as a whole

This study will be monitored by a Data and Safety Monitoring Board (DSMB). [name] [name] is a board-certified neurologist with full clinical privileges. She will serve as the Independent Medical Monitor. [name] is independent of NIB and will be involved in crucial decision making regarding clinical issues that may arise during this trial. We are instituting an NIB independent medical monitor as a way to mitigate [name] conflict of interest (COI). [name], the PI on the study, is co-inventor on an NIH patent related to the use of idebenone and as such will receive patent royalty payments.

16.2 DSMB plans

16.2.1. The proposed members of the DSMB are as follows:

We will utilize the same DSMB that is currently monitoring IPPoMS trial: [name] (DSMB chair) and [name] from MS Center of excellence, East, VA, Baltimore, MD, [name] from Georgetown University MS center and [name], MD from MS research group, University Hospital Basel, Switzerland

16.2.2. Role of DSMB:

Monitor/review AEs on a yearly basis and SAEs within 7 days of occurrence

16.2.3 Proposed meeting frequency/ schedule:

The DSMB will meet on a yearly basis via teleconference. Yearly AE data and clinical data will be collected and provided to the DSMB for review. Additionally, all SAEs will be communicated to the DSMB within 7 days of occurrence.

16.3 Criteria for stopping the study:

All SAEs will be communicated to the DSMB within 7 days of occurrence. The DSMB will decide on further action.

17. QUALITY ASSURANCE (QA)

17.1 Quality assurance monitor

A Contract Research Organization (CRO) will monitor this protocol.

17.2 Quality assurance plan

On-site monitoring will be carried out by the CRO. An initial visit will be conducted by the CRO, following final approval of the protocol by the IRB and FDA. During the initial visit, the study team and the monitor determined the frequency of monitoring visits. The frequency was set at yearly. The sponsor via the CRO, will be responsible for providing adequate oversight of the investigation

to ensure adequate protection of the rights, welfare, and safety of human subjects and the quality and integrity of the resulting data.

18. REPORTING OF UNANTICIPATED PROBLEMS, ADVERSE EVENTS AND PROTOCOL DEVIATIONS

The Principal Investigator is responsible for detecting, documenting, and reporting unanticipated problems, adverse events (AEs), including serious adverse events (SAEs), and deviations in accordance with NIH policy, IRB requirements, and federal regulations. Relatedness to the research of all serious adverse events will be determined by the PI in consultation with the CD.

Serious unanticipated problems, serious adverse events (including deaths) that are not unanticipated problems, and serious protocol deviations will be reported to the IRB and CD as soon as possible and in writing not more than 7 days after the PI first learns of the event, unless immediate reporting is waived for specific serious adverse events as noted below. Not serious unanticipated problems and not serious deviations will be reported to the IRB and CD as soon as possible and in writing not more than 14 days after the PI first learns of the event. Written reports will be submitted in PTMS.

All adverse events, deviations, and unanticipated problems will be summarized and reported at the time of Continuing Review.

The following expected Serious Adverse Events will not be reported to the IRB immediately and within 7 days unless they occur at a rate or severity greater than expected:

Hospitalization for urinary tract and kidney infections

Hospitalization for falls resulting in injury

These SAE's will be summarized at the time of continuing review. Serious adverse events occurring at a greater severity or frequency than expected will be reported as Unanticipated Problems as delineated above. The expected severity and frequency will be based upon each patient's pre-randomization history (baseline).

The NINDS, holder of the investigator-IND, or her/his representative is responsible for submitting reportable SAEs to the FDA under its private IND application, in accordance with Federal and NIH requirements. When a Serious Adverse Drug Reaction occurs during the clinical trial, the NINDS is also responsible for providing Santhera Pharmaceuticals (Switzerland) Ltd. or designee with a) primary safety information (i.e. short description including at least patient's number, age and gender; reported SAE terms and causality assessment) at the same time the NINDS clinical director and head of IRB are informed and no later than by Day 4 and b) copies of all Serious Adverse Drug Reaction reports concurrently with their submission to the FDA, including copies of any warning letters or other information affecting the safety and/or well-being of human subjects in research conducted under this MCRADA.

Santhera Pharmaceuticals (Switzerland) Ltd. is responsible, in collaboration with UBC Geneva, for the processing of reportable SAEs received from the NINDS or her/his representatives. Santhera is also responsible for the submission of those reportable SAEs to Health Authorities (other than the FDA), Ethics Committees and Investigators taking part in clinical trials with the same investigational

medicinal product, as required by regulations. Moreover, Santhera Pharmaceuticals (Switzerland) Ltd. will transmit to the NINDS all reports of Serious Adverse Drug Reaction occurring in Santhera-sponsored clinical trials and assessed as causally related to the investigational medicinal product, as well as any other information altering the safety profile of the study drug.

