Patients will be physically examined by the investigator approximately every 6 months for the study duration. One week, one month (Mo 25) and 2 months (Mo 26) after initiation of dosing, patient's safety and change in neurological function will be assessed by telephone interview with an investigator (Figure 2).

Extensive laboratory monitoring (CBC with differential and Chemistry panel 20, which includes LFTs) will occur three times during the study duration: at month 25, 30, and 36 (Figure 2). Urinalysis and pregnancy test (for females with childbearing potential) will be performed every 6 months (before MRI).

All adverse events occurring within 1 month following the last administration of the study medication must be recorded on the Adverse Event Form irrespective of severity and seriousness, and whether or not they are considered related to the study medication. Additionally, all serious adverse events (SAE) brought to the attention of the investigator during the period starting from the day of performance of the first study procedure to the telephone interview on month 37, must be recorded and reported to the FDA in accordance with federal regulations and NIH procedures. Any SAE reported by the patient after month 37, will be subjected to expedited reporting only if judged to be related to the study treatment by the Investigator.

The collection of complete and accurate information is of paramount importance to allow a full evaluation of SAEs. Each SAE will be properly documented and followed up until the event is resolved, subsided, stabilized, disappeared or is otherwise explained or the study patient is lost to follow-up. Recurrent episodes, complications, or progression of the initial SAE will be reported as follow-up to the original episode, regardless of when the event occurs. Follow-up of reportable SAEs will be submitted to the FDA, IRB and Santhera Pharmaceuticals (Switzerland) Ltd. according to the

same timelines mandatory for initial reports, i.e. within 7 calendar days for fatal/life-threatening and 15 calendar days for all other SAE. An SAE that is considered completely unrelated to one previously reported, will be reported separately as a new event.

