9.2.4 Assessment of causality

Every effort should be made by the investigator to explain each adverse event and assess its causal relationship, if any, to the study medication. The degree of certainty with which an adverse event can be attributed to the study medication (or alternative causes, e.g. natural history of the underlying diseases, concomitant therapy, etc.) will be determined by how well the event can be understood in terms of one or more of the following:

- Reaction of similar nature having previously been observed with this type of medication.
- The event having often been reported in literature for similar types of medication.
- Subject's underlying clinical state or other medical conditions
- Concomitant agents and/or therapies

The causal relationship, if any, to study medication will be defined by one of the following terms:

Assessment	Definition
Definitely	There is suspicion of a relationship between study medication and AE (without determining the extent of probability); there are no other more likely causes and study medication is suspected to have contributed to the AE
Probable	AE cannot be reasonably explained by other factors (i.e. clinical condition, environmental/toxic factors or other treatments)
Possible	AE can be reasonably explained by other factors (as mentioned above)
Unlikely	AE occurs within an unusual time frame of administration of study medication and can also be reasonably explained by other factors (as mentioned above)
Unrelated	There is no suspicion that there is a relationship between study medication and adverse event, there are other more likely causes and study medication is not suspected to have contributed to the AE

9.2.5 Treatment of adverse events:

Treatment of any AE is at the sole discretion of the investigator and according to current available best treatment. The applied measures will be recorded in the patient's chart.

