22. CONFLICT OF INTEREST/TECHNOLOGY TRANSFER

NIH guidelines on conflict of interest have been distributed to all investigators.

[name] has identified a conflict of interest related to this study. She is one of the co-inventors on an NIH patent related to the use of idebenone as therapeutic agents in humans. This conflict of interest is properly disclosed in the protocol and in the consent form.

To resolve this conflict-of-interest, we have instituted following safeguards:

- [name] will not obtain informed consent and will not serve as the treating or evaluating physician on this protocol.
- [name], a senior NINDS neurologist who is not part of the NIB, will serve as the Independent Medical Monitor under this protocol.
- The independent DSMB will monitor the study.

No other investigators identified any additional conflicts of interest.

A Cooperative Research and Development Agreement (CRADA) with Santhera Pharmaceuticals has been drafted through the NIH/NINDS office of technology transfer (OTT). This agreement specifies that Santhera will provide idebenone without restriction for the clinical study as outlined and will provide \$140,000 supplement for partial coverage (estimated $\geq 50\%$) of patient travel cost. All collected raw data will be the sole property of NINDS. Summary data will be made available to Santhera Inc. for regulatory purposes and for commercial purposes. Santhera Inc. can use these summary data for other purposes only after consultation with NINDS and only under confidentiality agreement.

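### Section 18 gives the relatedness decision for every SAE to a PI who will receive idebenone royalties, and the section 22 safeguards add oversight without moving that decision

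*Combined protocol and SAP*

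**What the plan says.** Section 18 of the combined protocol and SAP names who decides whether an SAE is related: "Relatedness to the research of all serious adverse events will be determined by the PI in consultation with the CD". The abbreviation CD is not expanded in that sentence. Elsewhere, section 18 refers to the NINDS clinical director, which is presumably who is meant.

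Section 16.1 discloses the conflict: the "PI on the study, is co-inventor on an NIH patent related to the use of idebenone and as such will receive patent royalty payments". It introduces an Independent Medical Monitor to mitigate that conflict and describes the role in general terms: the Monitor "will be involved in crucial decision making regarding clinical issues that may arise during this trial".

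Section 22 lists three safeguards:

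- The conflicted person "will not obtain informed consent and will not serve as the treating or evaluating physician on this protocol".
- The Monitor is "a senior NINDS neurologist who is not part of the NIB, will serve as the Independent Medical Monitor under this protocol".
- The independent DSMB monitors the study.

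Section 22 also records that no other investigator declared a conflict.

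Causality to the drug is handled elsewhere and by a differently named role. Section 9.2.4 says: "Every effort should be made by the investigator to explain each adverse event and assess its causal relationship, if any, to the study medication".

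**The concern.** The plan recognises that the PI's interest is serious enough to keep the PI away from consent, treatment and patient evaluation. Yet it leaves the PI with the relatedness judgement on every SAE. Consulting the CD adds a second opinion but does not transfer the decision.

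The design makes this label more important than it would be in a randomised comparison. Extending the safety and tolerability data is the first primary goal (section 5.2). The study is single-group and open-label (section 3.3), and safety is to be analysed descriptively (section 11.2). With no concurrent control arm, a reader who wants to know whether SAEs have anything to do with the research depends more on the assessor's judgement. What is at stake is the credibility of that reported judgement, since the person assigned to make it has a financial interest in the drug.

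**Working it through.** No figure in the plan is in dispute and no arithmetic applies. The check sets the relevant sections side by side and asks two questions: does any safeguard move the judgement, and what depends on it?

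**1. Is the conflicted person in section 22 the PI?** Names are removed from the text of section 22. Section 16.1 identifies the PI as a co-inventor on the idebenone patent, and section 22 describes the conflicted person as a co-inventor on such a patent and reports no other conflicts. The link therefore rests on section 16.1, and it is sound.

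**2. Does any safeguard reach SAE relatedness?**

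| Safeguard | What the text gives | SAE relatedness named or reassigned? |
|---|---|---|
| Role restrictions (22) | PI does not consent, treat or evaluate patients | No |
| Independent Medical Monitor (16.1, 22) | Part in important clinical decisions | No |
| DSMB (16.2, 16.3, 22) | Yearly AE review, every SAE within 7 days, decides further action | No |
| Consultation with CD (18) | Advice to the PI | Named, but the PI still decides |

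The safeguards provide oversight of events. None assigns the label to a non-conflicted person or asks anyone to review it.

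**3. Which steps depend on the section 18 label?**

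| Step | Section | Conditional on the section 18 label? |
|---|---|---|
| Recording AEs up to 1 month after last dose | 9.1.2 | No; required whatever the relationship to the drug |
| Recording SAEs and reporting them to the FDA, to month 37 | 9.1.2 | No relatedness condition is stated |
| Written IRB report of SAEs within 7 days | 18 | No; the exception for two expected hospitalisation types turns on rate or severity |
| DSMB receipt of SAEs within 7 days | 16.2.3, 16.3 | No |
| Relatedness to the research as reported for each SAE | 18 | Yes; this is the label itself |

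Only the last row is affected.

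**4. Is drug causality the same judgement?** No. Section 18 concerns relatedness to the research. Sections 9.1.2 and 9.2.4 concern the relationship to study treatment or medication, and give that call to the investigator. Within section 9 the same term describes the person who sees and treats patients: "Patients will be physically examined by the investigator approximately every 6 months for the study duration" (9.1.2), and "Treatment of any AE is at the sole discretion of the investigator" (9.2.5). Section 22 bars the conflicted PI from treating and evaluating, so the investigator in section 9 is probably someone else. The text does not say so, and that gap can be closed with the same edit.

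**The case against.** The strongest case against is that the matter is already handled. The CD is consulted. The Monitor was put in place specifically because of this conflict, and a part in important clinical decisions could reasonably cover a contested SAE. The DSMB sees every SAE within 7 days whatever its label and decides what to do. The conflict is disclosed in both the protocol and the consent form. The bar on being an evaluating physician most naturally means clinical evaluation of patients, so it can stand alongside the PI's reporting duties without contradiction. The study has also been stopped for futility with enrolment closed (section 7.6.1), so a wording change has little left to govern.

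Much of this stands. It is why the point is minor and why sections 18 and 22 are better described as sitting uneasily together than as contradictory. It does not answer the narrower point: oversight of events is different from deciding who assigns the label, and no section gives that task to a non-conflicted person. Stopping the study shifts the emphasis to labels already recorded and to any remaining SAEs. A final visit with safety laboratory work is still required, and the data move to protocol 09-N-0032 for continued analysis.

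A reader might infer a larger consequence: that the section 18 rule lets the PI control expedited reporting of SAEs after month 37 and the Day 4 Serious Adverse Drug Reaction notice to the supplier, or that it undermines statements such as the one in section 8.1 that the parent trial's five SAEs were judged not due to study medication. The documents do not support this. All three concern causality to the drug, which sections 9.1.2 and 9.2.4 give to the investigator, probably not the PI. Section 18 ties no reporting step to its own label, and the documents do not say who judged the parent-trial events.

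**Conclusion.** The point holds as a minor one, with medium confidence. Section 18 assigns SAE relatedness to the research to a person with a declared financial interest in the drug, and none of the listed safeguards reassigns it. Its reach is one reported attribute, for every SAE, in an uncontrolled study where safety is the first primary goal. Event capture and the main reporting routes are protected.

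No bias is shown and none can be sized, because the documents give neither the number treated nor the number of SAEs in this extension. It would be wrong to read the finding as evidence that any SAE has been mislabelled.

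The conclusion rests on two readings: that the conflicted person in section 22 is the PI described in section 16.1, and that the Monitor's general remit does not include setting or countersigning the relatedness label. Section 12.4, on investigators, was not in the text available for this review and may bear on who holds which role.

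**What to change.** - **Section 18:** state that a non-conflicted investigator already on the study, or the existing Independent Medical Monitor, makes or countersigns the determination of SAE relatedness to the research.
- **Sections 9.1.2 and 9.2.4:** state that, for causality to study medication, the investigator does not include the conflicted PI.
- **SAEs already recorded:** have the same non-conflicted person countersign any label the PI set, before final safety reporting.

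The wording change is one sentence in section 18 with matching text in 9.1.2 and 9.2.4. No new appointment is needed, since the Monitor is in place and no other investigator declared a conflict. The running cost is one sign-off per SAE. The seven-day reports to the IRB and DSMB are not conditional on the label, so they need not wait for it. Reviewing the recorded SAEs is separate, one-time work, and its volume cannot be stated because the SAE count is not given.
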